#### 4.10. Safety Analyses

Safety analyses will be conducted using the safety population.

There will be separate reporting for SAD and MAD, with all treatment groups. No total column will be provided. In general, SOC and PT will be presented alphabetically.

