| Objectives: | Primary: To evaluate the safety and tolerability of QR-010 administered via inhalation and identify the maximum tolerated dose (MTD). Secondary: To evaluate the change from baseline analysis for laboratory parameters and vital signs as well as the pharmacokinetics (PK) of QR-010 administered via inhalation. Exploratory: To explore the efficacy of QR-010 administered via inhalation. | |
| Study Design: | Randomized, double-blind (investigator and subject), placebo-controlled, single ascending and multiple ascending dose-escalation study. This study includes two portions: four single ascending dose (SAD) cohorts (1-4) and four multiple ascending dose (MAD) cohorts (5-8). An independent Data Safety Monitoring Committee (DSMC) will be designated to review all safety data at the end of each cohort. Safety data will include 7 days of follow up after the dose administered for SAD cohort subjects, and 7 days after the last dose administered for MAD cohort subjects. Initiation of the first MAD dose cohort will be based on the determination of the DSMC that an adequate safety profile has been demonstrated in the first two SAD cohorts. Similarly, subsequent MAD dosing cohorts will be initiated based on the determination of the DSMC that an adequate safety profile is demonstrated in the corresponding supportive SAD and MAD cohorts. Lastly, the DSMC will review safety data on an ad hoc basis. The type of adverse event (AE) that would trigger such an ad hoc DSMC review would be documented in the data safety monitoring plan. | |

| | |

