4.0 STUDY OVERVIEW

4.1 Criteria for Evaluation

4.1.1 Primary Endpoint

- Incidence and severity of adverse events (AEs) from baseline through end of study
- Occurrence of dose-limiting toxicities (DLT) in each dose cohort from baseline through end of study

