13.4 Analysis of Populations

Due to its exploratory nature, the analyses for this study will be mainly descriptive. If inferential statistics are provided they will be interpreted as hypothesis generation. Data analysis will be based on descriptive statistics for the dose groups, and when appropriate, pooled across dose groups. For continuous variables, the statistics include the following: geometric mean, mean, median, log-scale standard deviation, standard error of the mean, minimum and maximum. For categorical variables the statistics include frequency and proportions.

Screened: All subjects with an informed consent date will be part of this population.

Randomized: All subjects with a randomization date.

Safety Population: the population for safety analysis will consist of all subjects who receive any QR-010 or placebo. Subjects will be considered in the actual treatment received.

Exploratory Analysis Population: the population for efficacy (clinical activity) analysis will consist of all subjects randomized who receive at least one dose of QR-010 or placebo. Subjects will be considered in the actual treatment received.

Pharmacokinetics (PK) Population: will consist of all subjects who receive QR-010 and who have sufficient drug concentration measurements in blood samples or urine or sputum. This population will be used for PK analysis.

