13.10 Exploratory Efficacy Analyses

The exploratory clinical efficacy endpoints for the study will be evaluated for subjects enrolled in MAD cohorts. The exploratory efficacy evaluations will include:

- Pulmonary function
- Body weight
- CFQ-R RSS
- Sweat chloride

Descriptive statistics of clinical efficacy will be tabulated by dose group.

All continuous endpoints will be summarized using the following descriptive statistics: number of subjects, mean, standard deviation, standard error, median, minimum and maximum and 95% confidence intervals for the mean. Categorical endpoints will be summarized using: number of subjects, frequency, percentages and the 95% confidence intervals.

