## **4. STATISTICAL METHODS**

### **4.1. Sample Size Justification**

This is a Phase 1 safety study designed to evaluate the safety, tolerability and PK of QR-010. The sample size is not based on power calculations. It is chosen based on clinical experience and considered to be adequate to fulfill the objectives of the study.

Approximately 64 subjects will be enrolled in the study, with 8 subjects per cohort (6 QR-010 and 2 placebo), 32 each in the SAD and MAD portions of the study. The exact number of subjects enrolled is dependent on whether any dose levels are to be expanded due to the occurrence of AEs of interest.

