#### 4.10.1.3. DLT definition

Potential DLTs are reviewed and adjudicated by the DSMC. Adjudicated DLTs will be loaded from an excel file and summarized by treatment group. Individual subject listings will be provided for each DLT including severity.

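### SAP 4.10 shows adverse-event incidence only by placebo and single dose, with no interval and no combined QR-010 column, so this part of the primary endpoint is reported less precisely than the data allow

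*SAP*

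**What the plan says.** Under Safety Analyses (4.10) the SAP states: "There will be separate reporting for SAD and MAD, with all treatment groups". It then adds: "No total column will be provided". TEAEs (SAP 4.10.1.1) and FEV1 falls of 15% or more (SAP 4.10.1.4) are summarised by treatment group. For dose-limiting toxicities, SAP 4.10.1.3 says: "Adjudicated DLTs will be loaded from an excel file and summarized by treatment group". SAP 4.2.8 specifies number and percentage for categorical variables; no interval is named for any safety incidence.

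The table headers (SAP Tables 3 and 4) have one placebo column, four dose columns and an optional total. SAP 4.2.5 shows that total in general for disposition, baseline and exposure. No header has a column for all QR-010 subjects.

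The first primary endpoint in protocol 4.1.1 is "Incidence and severity of adverse events (AEs) from baseline through end of study". The second is DLT occurrence, defined within each dose cohort. Protocol 13.4 bases the analysis on descriptive statistics for the dose groups, "and when appropriate, pooled across dose groups". The planned size is "8 subjects per cohort (6 QR-010 and 2 placebo), 32 each in the SAD and MAD portions of the study" (SAP 4.1).

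**The concern.** Safety is the primary question, and its main tables will set groups of about six against about eight placebo subjects. A bare zero out of six is easily read as a clean result, yet it is compatible with a high true rate. Zero of six is also a category in the escalation table (protocol Table 3, SAP Table 2), so it may well be a headline result.

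The shells already combine placebo over the four cohorts of a part but never combine active drug. Elsewhere the sponsor accepts that combining small groups helps: SAP 4.8.2.1 pools first-day ppFEV1 over SAD and MAD for robustness. The post hoc SAP adds efficacy analyses only, so it leaves this gap open.

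**Working it through.** **Inputs.** Eight subjects per cohort, 6 on QR-010 and 2 on placebo (SAP 4.1; protocol 13.2). Four SAD and four MAD cohorts (protocol synopsis). Doses 6.25, 12.5, 25 and 50 mg. The documents give no event rates, so the rates below are assumptions.

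**Planned numbers.** 8 cohorts × 8 = 64 in total and 4 × 8 = 32 per part, as stated. Per part this gives 4 × 6 = 24 on QR-010 and 4 × 2 = 8 on placebo. If every cohort is expanded by four, 8 × 12 = 96, which matches protocol 5.2.

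**Precision.** Exact (Clopper-Pearson) two-sided 95% intervals. For zero events the upper limit is 1 − 0.025^(1/n):

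- n = 6: 1 − 0.025^(1/6) = 45.9%
- n = 8 (placebo): 1 − 0.025^(1/8) = 36.9%
- n = 24: 1 − 0.025^(1/24) = 14.2%

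| Observed | One dose (n = 6) | All QR-010 (n = 24) |
|---|---|---|
| No events | 0 to 45.9% | 0 to 14.2% |
| One event | 0.4 to 64.1% | 0.1 to 21.1% |
| Half the subjects | 11.8 to 88.2% | 29.1 to 70.9% |

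**Chance of seeing at least one event**, 1 − (1 − p)^n, with the same rate p at every dose:

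| Assumed rate | n = 6 | n = 24 |
|---|---|---|
| 5% | 26.5% | 70.8% |
| 10% | 46.9% | 92.0% |
| 20% | 73.8% | 99.5% |

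**Comparison with placebo.** At an assumed 20% rate in both groups, the standard error of the difference is √(0.16 × (1/6 + 1/8)) = 0.216 for one dose and √(0.16 × (1/24 + 1/8)) = 0.163 for all QR-010. That is a fall of 24%, but 1.96 × 0.163 is still about ±32 percentage points.

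**What pooling cannot do.** Suppose an event occurs in 10% of subjects at 50 mg and never at lower doses. The chance of seeing it is 1 − 0.9^6 = 46.9% with or without a pooled column, and the pooled rate being estimated is 10%/4 = 2.5%. After zero in 24, the 50 mg group on its own is still zero in 6, with an upper limit of 45.9%.

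**The case against.** Several stronger readings are tempting, and the documents do not support them.

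- *That SAP 4.10 forbids any combined column.* The only total the SAP defines stands after the placebo and dose columns and appears to include placebo. Leaving it out of safety tables is reasonable, because it would mix active drug with control. The sentence says nothing about an active-only column, and deleting it would not produce one.
- *That the SAP departs from the protocol.* Protocol 13.4 is permissive. Protocol 13.7.1 to 13.7.4 specify TEAEs, DLTs, vital signs and laboratory data by dose, and SAP 4.10 follows them.
- *That DLTs should be pooled too.* The DLT endpoint is defined per dose cohort and the MTD is dose-specific. Six per dose is that endpoint's own unit.
- *That readers cannot rebuild pooled results.* Counts add, including the FEV1-fall counts. Means, SDs and extremes combine from the planned statistics. Only medians and quartiles do not.
- *That efficacy gets intervals and safety is denied them.* Protocol 13.10 does ask for "percentages and the 95% confidence intervals" for categorical endpoints, but the four endpoints it lists are continuous measures. The contrast carries little weight.

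It is also true that no escalation decision depends on these tables: the DSMC reviews unblinded data and applies count rules. The synopsis rules out inferential testing, but an exact interval is not a test, and protocol 13.10 lists intervals among descriptive summaries.

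All of this limits the point to reporting. It does not remove it: AE incidence is not defined per cohort, and nothing in the plan shows how imprecise each percentage is.

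**Conclusion.** The point holds as an inexpensive improvement to how AE incidence is reported. It is not an error or a protocol breach. As planned, a zero at one dose will be printed with no sign that rates up to 45.9% remain compatible with it, while the combined QR-010 data in the same part could bound the average rate at 14.2%.

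These figures rest on the planned 6 and 24. Expansion would raise them, and early stopping of escalation would lower them. The 14.2% limit and the 92.0% detection chance describe a particular dose only if rates are equal over an eightfold dose range, which nobody knows in a first-in-human trial. A reader might infer that zero in 24 clears the top dose; it does not. For DLTs the gain is the interval at each dose, not the pooling.

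**What to change.** Keep the exclusion of a total that includes placebo, and add to SAP 4.10:

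*For SAD and MAD separately, an All QR-010 column will be shown beside Placebo and each dose column in the AE, AESI and FEV1-fall incidence tables, as a supplement to the by-dose results.*

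Add exact (Clopper-Pearson) 95% confidence intervals to the rows for overall TEAEs, Grade ≥2 TEAEs, related TEAEs, AESIs and FEV1 falls, and to the by-dose DLT rows. DLTs stay by dose cohort, and any pooled DLT rate is supplementary only. Pool within each part and not across them, because protocol 5.5.1 lets SAD completers enter a MAD cohort.

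The cost is one column, a few rows and a little programming, with no new data and no effect on conduct. The drawback is that a rate pooled over 6.25 to 50 mg can dilute a top-dose effect, so the column must never replace the dose columns. If the tables are already final, protocol 13.1 allows the addition as a clearly identified unplanned analysis in the study report.

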#### 4.10.1. Adverse Events

##### 4.10.1.1. General Adverse Event Reporting

Adverse events will be summarized with MedDRA System Organ Class (SOC) and Preferred Term, by subject incidence rates, therefore, in any tabulation, a subject contributes only once to the count for a given adverse event (SOC or preferred term or AESI).

A treatment emergent Adverse Event (TEAE) is defined as an event with start date at/or after first dose.

An overall summary of TEAEs will include the number of

- Subjects with at least one TEAE,
- Number of TEAE,
- Subjects with study drug-related TEAEs,
- Subjects with device-related TEAEs,
- Subjects with TEAEs by maximum severity grade,
- Subjects with serious AEs,
- Subjects with TEAEs Leading to Treatment Discontinuation,
- Subjects with TEAEs Leading to Study Discontinuation,
- Deaths

The overall incidence of TEAEs will be summarized by treatment group and classified by SOC and PT. Reporting will include reports for Serious AEs, AEs leading to treatment discontinuation, deaths, AEs related to study drug, AEs related to device. AEs by SOC and PT will be presented by maximum severity.

An AE will be considered drug-related if the Investigator or Sponsor indicated that the event is coded "possibly" or "definitely" related to study drug or if the relationship is missing. The same definition applies for relationship to device.

AE intensity is graded on a 5 level category (Mild/Grade 1, Moderate/Grade 2, Severe/Grade 3, Life threatening/Grade 4, Death/Grade 5). Maximum intensity per PT is reported.

TEAEs will be listed in subject listings. Listings of Serious TEAEs, Death, Grade 2 or higher TEAEs will also be presented.

A listing for the non-treatment emergent events (with start date and time prior to first dose) will be provided, the listing will be provided only if events are collected.

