3.2 Secondary Objective(s)

The secondary objectives of the study are:

- To evaluate the change from baseline analysis for laboratory and vital signs
- To evaluate the pharmacokinetics (PK) of QR-010 administered by inhalation.

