13.7.3 Vital Signs

Vital sign measurements will consist of respiratory rate, pulse, blood pressure, temperature and oximetry. Descriptive summaries (number of subjects, mean, standard deviation, median, minimum, and maximum) of actual values and changes from baseline will be presented for each time point. These summaries will be presented for the safety population and by dose group.

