#### 4.2.7.5. Vital Signs and Weight

**Table 18: Time points for Vital Signs SAD**

Time point	Target	Interval for Analysis
Baseline	Day 1 dose start time	Most recent value prior to first dose
Day 1 1min Post-dose	Day 1 dose end time+1min	]Day 1 dose end time, Day 1 dose end time+5min]
Day 1 10 min Post-dose	Day 1 dose end time+10min	]Day 1 dose end time+5min, Day 1 dose end time+20min]
Day 1 30min Post-dose	Day 1 dose end time+30min	]Day 1 dose end time+20min, Day 1 dose end time+45min]
Day 1 60min Post-dose	Day 1 dose end time+60min	]Day 1 dose end time+45min, Day 1 dose end time+90min]
Day 1 2hrs Post-dose	Day 1 dose end time+2h	]Day 1 dose end time+90min, Day 1 dose end time+3h]
Day 1 4hrs Post-dose	Day 1 dose end time+4h	]Day 1 dose end time+3h, Day 1 dose end time+8h]
Day 1 12hrs Post-dose	Day 1 dose end time+12h	]Day 1 dose end time+8h, Day 2[
Day 2	Day 2	[Day 2, Day 3[
Day 3	Day 3	[Day 3, Day 4[
Day 4	Day 4	[Day 4, Day 7[
Day 8	Day 8	[Day 7, End of Study]

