#### 4.10.3. Vital Signs and Oximetry

Descriptive summaries of actual values and changes from baseline of vital signs will be reported for each time point, in the following parameters: Height (baseline only), Weight, BMI, Heart rate, Systolic and Diastolic Blood Pressure, Temperature, Pulse rate and Pulse Oximetry.

By-subject listings of vital sign measurements will be presented including flag for abnormality (if exist). A special listing reporting vital signs measurements considered clinically relevant will be provided.

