## **5. CHANGES TO PLANNED ANALYSES**

As of this date, there have been no changes between the protocol-defined statistical analyses and pharmacokinetics analyses those presented in this statistical plan.

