
Abbreviations: C = complete physical exam; H = height; S = symptom-directed physical exam; U = urinalysis (dipstick); W = weight
 
a The screening period for an individual subject may be extended for an additional 7 days at the discretion of the Sponsor's Medical Monitor. See Protocol Section 7.2 for details.
 
b See Protocol Section Section 7.3.2 for details on timing of these assessments relative to study drug administration on Day 1.
 
c Includes blood pressure, heart rate, respiratory rate, and temperature.
 
d Includes FEV1, FVC, and FEF25-75.
 
e A Chest Xray or CT scan obtained within 90 days of screening is acceptable if there was no intercurrent pulmonary illness during the interim.
 
f Only subjects who experience pulmonary AEs during the study.
 
g See Protocol Appendix 2 for a detailed schedule of these assessments, broken down by type of specimen and time relative to dose.
 
h Only laboratory assessments that are abnormal (but not clinically significant) at screening should be repeated at Day-1.
 
i Pregnancy test (preferably serum but urine is accepted) required for women of childbearing potential only.
 
j Subjects who are taking concurrent CF therapy should receive this therapy prior to study drug dosing in the order specified in Protocol Section 6.3.1.
										

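### The SAP declares no changes from the protocol, but it drops respiratory rate from the vital-sign summaries and has no rule for adverse events with a missing start date

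*SAP*

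**What the plan says.** **Declaration.** SAP section 5 reports that "there have been no changes between the protocol-defined statistical analyses and pharmacokinetics analyses those presented in this statistical plan". SAP 1.2 makes this plan the basis of the CSR results. The later post hoc plan covers efficacy only and does not amend the safety rules.

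**Vital signs.** Protocol 13.7.3: "Vital sign measurements will consist of respiratory rate, pulse, blood pressure, temperature and oximetry". It asks for descriptive summaries "of actual values and changes from baseline will be presented for each time point". The SAP 4.10.3 summary list has height, weight and BMI, then "Heart rate, Systolic and Diastolic Blood Pressure, Temperature, Pulse rate and Pulse Oximetry". The SAP's own schedule footnote on vital signs (Table A.1-1, repeated for the MAD cohorts) reads "Includes blood pressure, heart rate, respiratory rate, and temperature".

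**Treatment-emergent AEs.** SAP 4.10.1.1: "A treatment emergent Adverse Event (TEAE) is defined as an event with start date at/or after first dose". TEAEs are listed, and a second listing takes events that began before the first dose. Protocol 13.7.1 is wider. It adds exacerbations of events present before dosing, counts as emergent an AE with no start date whose stop date runs into the treatment period, and says that every AE will be listed.

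**Hypoxia.** Protocol Table 2 (section 4.3) describes hypoxia of interest as Grade 2 or higher: desaturation on exercise, with a reading under 88% as an example, or intermittent supplemental oxygen. SAP 4.10.1.2.8 (AESI8) uses only an oximeter reading under 88%.

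**The concern.** A reader who trusts section 5 will assume that the CSR safety tables follow protocol section 13, and on two points they will not.

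The second protocol secondary-objective group begins with safety: "To evaluate the change from baseline analysis for laboratory and vital signs". Respiratory rate is one of those vital signs and is directly relevant to an inhaled product with no earlier clinical studies. AE incidence is a primary endpoint, so the rule that decides which events count as emergent matters more than a formatting choice.

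Protocol 13.7.5 leaves urinalysis, ECG and physical examination to the SAP. It does not leave vital signs or the TEAE definition to it, so delegation does not explain either difference.

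**Working it through.** The plan gives no figure to reproduce. The check sets the rules side by side, counts what is affected, and adds simple fractions.

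**1. Respiratory rate**
- Protocol 13.7.3 set: respiratory rate, pulse, blood pressure, temperature, oximetry = 5. All but respiratory rate appear in SAP 4.10.3, so 1 of 5 has no planned summary.
- Planned subjects: 32 SAD + 32 MAD = 64.
- SAD windows ("Table 18: Time points for Vital Signs SAD"): baseline 1 + Day 1 post-dose 7 + Days 2, 3, 4 and 8 (4) = 12.
- MAD windows (SAP Table 20): baseline 1 + Day 1 (7) + Day 3 (8) + Day 4 (1) + Day 5 (6) + Day 8 (6) + Days 10 and 12 (2) + Day 15 (6) + Days 17 and 19 (2) + Day 22 (6) + Day 24 (1) + Day 26 (6) + Days 33 and 54 (2) = 54.
- Five of the six Day 26 windows are post-dose, while protocol 7.4.9 asks only for vital signs within 2 hours after dose 12. So 54 counts analysis windows, not scheduled measurements.

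**2. An AE with no start date whose stop date runs into treatment**

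| Output | Condition | Included? |
|---|---|---|
| Protocol 13.7.1 TEAE tables | Explicit missing-date rule | Yes |
| Protocol 13.7.1 listing | All AEs | Yes |
| SAP TEAE tables and listing | Began on or after first dose | No, cannot be shown |
| SAP non-emergent listing | Began before first dose | No, cannot be shown |
| SAP reports not worded as TEAE-only | Serious, related, SOC/PT by maximum severity | Possibly |

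The exacerbation clause is also absent from the SAP. However, protocol 12.4.3 has a worsened persistent AE entered again and a worsened pre-existing condition recorded as an AE. If the new record carries a post-dose start date, the SAP rule catches it, so few or no counts should change.

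**3. Hypoxia**
- Protocol Table 2 has 8 AEs of interest. The SAP keeps 6 as Grade 2 or higher events by preferred term (AESI1, 2, 3, 5, 6, 7). One is laboratory-based in both documents (AESI4). One becomes a reading alone (AESI8).
- Protocol 8.4 has oximetry measured seated at rest, so scheduled readings are not designed to capture exercise desaturation or oxygen use.
- A reported Grade 2 or higher hypoxia AE without a reading under 88% is therefore not counted as AESI8. With a post-dose start date it still appears in the TEAE tables and the Grade 2 or higher listing.

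**4. Weight of one uncounted subject with no other event in that table row**
- QR-010 dose group as planned: 1/6 = 16.7 percentage points.
- Pooled placebo within a part: 2 x 4 = 8, and 1/8 = 12.5 points.
- If every cohort is expanded (protocol 5.2, about 96 subjects, so 96/8 = 12 per cohort) and the added four are also split 3:1 (assumed): 1/9 = 11.1 points, and with placebo 3 x 4 = 12, 1/12 = 8.3 points.

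These fractions show the leverage of one subject. They do not estimate how many events would be missed.

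**The case against.** **Respiratory rate may be a drafting slip.** SAP 4.10.3 names both heart rate and pulse rate, and one may have been meant as respiratory rate. By-subject listings and a listing of clinically relevant values remain. This stands as an explanation, but tables are programmed from the text, and listings are not the summary that the protocol requires.

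**The TEAE gap has exits and should rarely matter.** Several reports in SAP 4.10.1.1 are not worded as TEAE-only, including the SOC/PT table by maximum severity. Protocol 8.1 has start dates recorded, and protocol 14.2 has omissions queried. All of this stands. A reader might infer that events vanish from the CSR; the documents support only that they can miss the TEAE tables and both listings.

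**AESI8 is not a third contradiction of section 5.** A reader might infer that it is. Section 5 speaks of the protocol's statistical analyses. Table 2 sits in the dose-escalation section, and protocol section 13 defines no analysis of AEs of interest. The SAP also plans an overall AESI summary, AESI listings and oximetry summaries, and a reading-based rule can catch desaturations never reported as AEs. What stands is that AESI8 omits part of the Table 2 definition.

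**Version.** SAP 1.1 cites protocol versions 8.0 to 8.2, and the version of the supplied protocol cannot be confirmed. The two laboratory schedules differ in places: for example, SAP Table A.2-2 has a separate urine PK sample at 24 and 72 hours after dose 1, while the protocol's table has 72 hours only. Version drift is therefore possible, though not shown.

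**Conclusion.** Two SAP safety rules differ from protocol section 13 while section 5 declares no changes. The respiratory-rate omission is definite on the text as written: no planned summary for 1 of 5 vital signs in either part. The TEAE gap is conditional on missing start dates, which should be rare. The number of affected events is unknown. AESI8 is a separate, narrower-definition point whose missed events remain visible elsewhere.

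A reader might also infer that dose escalation or the MTD is at risk. The documents do not support that. SAP 2.5.2 sends the DSMC AEs of interest as the protocol defines them, and DLTs are adjudicated by the DSMC (SAP 4.10.1.3). The effect is confined to final CSR tables and listings.

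Severity is low. The conclusion assumes that the supplied protocol matches the versions the SAP cites on these points, and that the SAP text is programmed literally.

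**What to change.** - Add respiratory rate to the SAP 4.10.3 summaries, and check whether heart rate and pulse rate are both intended.
- Copy the full protocol 13.7.1 TEAE rule into SAP 4.10.1.1, including exacerbations and missing start dates, and produce one listing of all AEs.
- Count AESI8 as a reading under 88% or a Grade 2 or higher hypoxia-type AE, and show the two sources separately.
- If any difference is intended, state and justify it in SAP section 5, and confirm the protocol version against which the SAP was written.

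The cost is SAP wording and a few lines of programming, with no new data. TEAE and AESI counts may rise slightly.
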